recovery and reduce falls. The programme includes *four* interventions that are based on best available evidence (i.e. falls prevention education, FaME group based exercise programme, Otago home exercise programme, and a home falls hazard evaluation) and *three* components that have not previously been investigated as part of multifactorial falls prevention approach (i.e. Exergames, safe landing/falls technique training - which includes teaching people how to move if on the floor and how to safely get up from the floor-, and a social activity undertaken after the exercise sessions). This programme aims to increase falls prevention knowledge, increase strength and balance, evaluate home falls hazards, teach individuals how to land safely in case of a fall, how to move on the floor and how to get up again. The delivery mode of the programme provides participants an opportunity to train and socially interact with support from a small group of peers. Feasibility of delivering this multifactorial programme requires investigation.

5. Study Aims and Objectives

Study Aim

The aim of this research project is to evaluate the feasibility of providing a newly developed multifactorial falls prevention programme for community-dwelling patients ($n = 10$) after stroke.

Study Objectives

- 1) to explore the participants' and the therapists' experiences (barriers, enablers) on the *acceptability* (e.g. appropriateness, satisfaction, safety), *implementation* (e.g. execution, factors affecting implementation ease) and *practicality* (e.g. ability of participants and staff to carry out the interventions) of the programme,
- 2) to explore whether participating in the programme can positively influence the participants' fear of falling, quality of life, balance and mobility and social engagement.

6. Method

Study Design

This is an exploratory mixed-method phase I feasibility study with a pre-post design.

Participants, Sample Size and Eligibility Criteria

A convenience sample of 10 patients after stroke will be recruited.

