The main method of recruitment consists of handing out information about the study and an example of the informed consent form to identified and potentially eligible participants. The Participant Information Statement (Appendix 8) and Consent Form (Appendix 9) for the study will be available only in English. Following receipt of the information about the study participants can contact the CI if they would like to participate.

People in the networks of the researchers can be active physiotherapists that know patients, and who may approach patients who they think are eligible to, and might benefit from, participation. To avoid the potential for coercion it will be made explicitly clear to these 'recruiting' active physiotherapists that when they hand out the Patient Information Statement

they must explain to each potential participant that they are not obliged to participate, and if they choose not to participate or withdraw after the start of participation, their medical care and legal rights will not be affected.

Consent procedures

Signed consent (Appendix 9) will be sought prior to the baseline assessment, and only when the researcher has ensured that the participant has accessed and understood the information provided. Each participant will be asked to sign two informed consent forms; one will be retained in the Investigator Site File, and one will be provided to the participant. The right to refuse or withdraw (from) participation without giving reasons will be respected.

7. Statistical Considerations

As this is a feasibility study the analyses will be primarily descriptive.

Quantitative data analysis

The quantitative data collected during this study (participant characteristics, participant questionnaires, physical tests, compliance, number of fall incidents, data completion) will be analysed and presented descriptively in terms of means (standard deviations), medians (interquartile ranges) and categories. Data completeness will also be ascertained of the instruments and any potential bias in the completion data to inform the choice of instruments in a future trial.

Qualitative data analysis

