All in-depth interviews will be recorded, fully transcribed verbatim, anonymised and coded. Transcripts will not be returned to participants for comments or corrections. The analysis will be performed using thematic analysis, which is a method for identifying, analysing and reporting patterns ('themes') within data.(41) Thematic analysis focuses on similarities and differences and results in the organisation of the data from codes into (candidate) themes (42). The analysis will be performed by two of the authors ([name], [name]) with all authors agreeing the final themes. Quotes illustrating each theme will be identified for use in the publication(s).

Assessment of the feasibility to progress to a full trial

Following the completion of the qualitative interviews the research team members will have a discussion about the practicality of the study design, its impact on and acceptability to, both patients after stroke and professionals, and the acceptability and applicability of the outcome measures for the intervention. The conclusions from this discussion will inform the development of a definitive RCT. The progression criteria to judge the feasibility of progressing to a full trial are:

1. $\geq 70\%$ of the participants complete 9 of the 12 group sessions (compliance)
2. $< 10\%$ of serious adverse events (SAEs) deemed due to the intervention.

8. Risks and benefits

Risks

During this research study the participants will be exposed to balance challenging exercises, and exercises that can result in muscular fatigue. Recent research has shown that older people are at increased risk of falling following intensive endurance exercise bouts,(43) through exercise induced alterations in respiration and muscular fatigue. The same will be true for people who have had a stroke. Increased muscular fatigue may exacerbate existing gait and balance difficulties, further increasing the risk of falls. It is therefore essential that participants are offered a targeted and appropriately balanced exercise programme which is gently increased in duration / exercise load.

Benefits

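### Progression criterion 2 has no clear denominator and neither criterion carries an interval, so a pass with 10 people does not by itself establish related-SAE risk below 10% or compliance of at least 70%

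*Combined protocol and SAP*

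**What the plan says.** All references are to the combined protocol and SAP.

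- **Design and size** (Section 6, Study Design and Participants, Sample Size and Eligibility Criteria): "This is an exploratory mixed-method phase I feasibility study with a pre-post design". "A convenience sample of 10 patients after stroke will be recruited". No sample-size or precision calculation is given.
- **Analysis** (Section 7, opening sentence and Quantitative data analysis): "As this is a feasibility study the analyses will be primarily descriptive". The data are to be "analysed and presented descriptively in terms of means (standard deviations), medians (interquartile ranges) and categories". No confidence interval is listed. The quantitative data named there include compliance and fall incidents but not SAEs.
- **Decision rule** (Section 7, Assessment of the feasibility to progress to a full trial): "The progression criteria to judge the feasibility of progressing to a full trial are", followed by two items. The first is at least 70% "of the participants complete 9 of the 12 group sessions (compliance". The second is under 10% "of serious adverse events (SAEs) deemed due to the intervention". A research-team discussion of practicality, impact, acceptability and outcome measures accompanies them.
- **Delivery** (Section 6, Intervention): two groups of five, taught by the same two professionals.
- **Withdrawal** (Section 8): participants may leave at any time, and the investigator may withdraw them, including after an AE or SAE. Section 7 does not say whether people who withdraw count in either percentage.

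**The concern.** Two things are wrong with the rule as a rule.

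First, criterion 2 puts SAEs in the denominator. The proportion of SAEs judged related is not a measure of risk to participants. It has no value when nothing serious happens, which is the best outcome for safety, and it becomes easier to satisfy as unrelated SAEs accumulate. A safety threshold should do neither.

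Second, both criteria are percentages from 10 people, and the plan provides nothing to show how imprecise they are. A report could state that both thresholds were met, and readers could take this as evidence that the underlying risk and compliance lie on the right side of 10% and 70%.

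The plain language summary (Section 2) says a definitive randomised trial will be proposed if this study suggests the programme can work. The programme includes training in how to fall, and fracture is among the expected adverse events in Section 9. The safety statement carried forward should therefore say what 10 people can and cannot show.

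**Working it through.** **Inputs.** n = 10 (Section 6). Criterion 1: at least 70%. Criterion 2: under 10% (both Section 7). The documents give no confidence level or sidedness, so 95% is an assumption, with both one- and two-sided limits shown where it matters. The plan states no precision figure to reproduce.

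**1. What counts as a pass on criterion 2.**

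As worded, with R related SAEs among S SAEs, a pass needs R/S < 0.10.
- S = 0: 0/0, undefined.
- R = 1, S = 10: 10%, fail.
- R = 1, S = 11: 9.1%, pass.

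The same single related event fails or passes according to how many unrelated SAEs occur.

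Per participant, with x of 10 people having a related SAE, a pass needs x/10 < 0.10. Because 1/10 = 10% is not below 10%, only x = 0 passes.

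**2. What 0/10 can exclude.**

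Exact (Clopper-Pearson) upper limit for zero events:
- two-sided 95%: 1 − 0.025^(1/10) = 30.8%
- one-sided 95%: 1 − 0.05^(1/10) = 25.9%

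Other methods give similar answers: Wilson (two-sided) 27.8%, rule of three 3/10 = 30%. With fewer evaluable people the two-sided exact limit rises to 33.6% (n = 9) or 36.9% (n = 8).

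The chance of passing when the true per-participant risk is p is (1 − p)^10:

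| True risk | Chance of 0/10 |
|---|---|
| 10% | 34.9% |
| 20% | 10.7% |
| 30% | 2.8% |

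Under the SAE-based wording, a pass with one affected participant is also possible. For 1/10 the two-sided exact upper limit is 44.5%.

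**3. What the minimum compliance pass shows.**

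The smallest pass is 7/10. The exact two-sided 95% limits are beta quantiles:
- lower: 2.5% point of Beta(7, 4) = 34.8%
- upper: 97.5% point of Beta(8, 3) = 93.3%

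Wilson gives 39.7% to 89.2%. The chance of passing is P(X ≥ 7) for X binomial with n = 10:

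| True compliance | Chance of at least 7/10 |
|---|---|
| 50% | 17.2% |
| 60% | 38.2% |
| 70% | 65.0% |
| 80% | 87.9% |

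**4. Why the denominator matters for criterion 1 too.**

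Suppose, for illustration, that two people withdraw and six of the remaining eight complete enough sessions. Counting everyone enrolled gives 6/10 = 60%, a fail. Counting only those who stay gives 6/8 = 75%, a pass.

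**5. Independence.**

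All these figures treat participants as independent. With two groups of five and shared instructors, outcomes within a group may be correlated, and the intervals may then be too narrow. The documents give no figure from which to size this.

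**The case against.** The strongest reply is that this is an exploratory, descriptive study of 10 people, and that the criteria are decision rules on observed data. Nowhere does the plan promise to show a population risk below 10% or population compliance of at least 70%. That is right, and the point concerns how a pass is defined and described. An interval is itself a descriptive summary and tests nothing.

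It is also fair to say that the decision does not rest on two numbers alone. A team discussion accompanies the criteria. Under Section 9, related AEs and SAEs go to all investigators and the ethics committee within five working days, and the team monitors trends. These safeguards stand. They neither define the denominator nor describe the uncertainty in the criteria.

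Three stronger readings are tempting, and the documents do not support them.

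- **That 31% is the most a pass on criterion 2 could conceal.** This holds only for a two-sided 95% limit, a per-participant reading and 10 evaluable people. Under the literal wording one related SAE can pass, and 1/10 has an upper limit of 44.5%.
- **That even perfect compliance could not support 70%.** For 10/10 the two-sided lower limit is 0.025^(1/10) = 69.2%, but the one-sided limit is 0.05^(1/10) = 74.1%, which clears the threshold. The answer depends on a convention that the plan does not fix.
- **That the safety rule is lax.** Read per participant it is strict: a true risk of 10% fails 1 − 0.349 = 65.1% of the time, and a true risk of 20% fails 89.3%.

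Finally, exact intervals from a convenience sample taught in two groups could suggest more authority than the design gives. That stands as a caveat to print with them.

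**Conclusion.** The point holds as an improvement to the decision rule and its reporting. Criterion 2 as worded is undefined with no SAEs and can be met by one related SAE among 11 or more. If a per-participant risk is intended, only 0/10 passes, and that result leaves true risks up to about 26% (one-sided) or 31% (two-sided) unexcluded at the 95% level. The minimum compliance pass is compatible with true compliance anywhere from about 35% to 93%. Meeting both criteria therefore does not by itself establish either threshold for the wider population.

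These sizes assume 10 evaluable, independent participants and a 95% level, which the documents do not specify. A reader might go on to infer that the plan contains a calculation error or that the study must be enlarged. Neither follows: the plan makes no precision claim that could be wrong, and 10 people can serve the stated feasibility aim if the criteria are clearly defined and modestly reported.

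**What to change.** In Section 7:

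1. The sponsor should confirm the intended denominator of criterion 2 and restate it per participant: the number of participants with at least one related SAE, out of all enrolled eligible participants including those who withdraw. State that with n = 10, under 10% means none, and record that this changes the literal wording.
2. Use the same denominator for criterion 1 and keep its 70% cut-off.
3. Report both criteria as x/n with exact (Clopper-Pearson) 95% intervals, noting that these assume independent participants although delivery is in two groups of five.
4. Describe a pass on criterion 2 as an observed result that does not exclude risks up to about 26% to 31%.

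Keep n = 10. The cost is a few sentences in Section 7 and two intervals in the report. The downside is a less favourable safety statement.

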Participants are eligible for participation if they 1) are over 50 and more than 6 months post-stroke, 2) live in the community, 3) have good cognition (MMSE ≥ 25 points) and 4) are able to walk at least three times weekly outside their home without hands on supervision (with or without the use of a walking aid). Participants will be excluded if they 1) have medical issues preventing them from participating in moderate to vigorous strength and balance exercises

and 2) have receptive aphasia impacting on ability to follow instructions and 3) are unable to provide informed consent.

Intervention

The programme delivered during this feasibility study will consist of a total of 12 multifactorial falls prevention group exercise sessions. Each session is 90-100 minutes in duration, followed by a 20-30 minute social activity (2 hours in total). The sessions will be offered over a period of 8 weeks, with one session in one week and two sessions in the next. Each session will comprise (a mix of) seven program components of the intervention:

1) *Falls prevention education*: Fifteen minutes of each session will be spent on an existing educational programme⁽²³⁾ that is framed on the principles of changes to health behaviour. This part of the programme is aimed to alert patients to their personal risk of falls, raise their knowledge about falls epidemiology and falls prevention. The educational information will be aimed specifically at patients after stroke.

2) *FaME group-based exercises* for strength and dynamic balance (these include some basic Tai Chi exercises). Fifteen minutes of every other training session will be spent on this part of the programme.

3) *(Preparing for) home exercises*. Selected components of both the FaME group-based exercise programme and the Otago home exercise programme will be practised in order to prepare participants to perform these at home for 10-20 minutes per day for the duration of the intervention.

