- 2) the Short Falls-Efficacy Scale-International (FES-I). The FES-I is a validated and reliable 7-item tool which measures confidence in performing a range of activities of daily living without falling.
- 3) The European Quality of Life 5 Dimensions Health Questionnaire (EQ-5D-5L)(32) measures health based on a descriptive system that defines health in terms of five dimensions: mobility, self-care, usual activities, pain/discomfort, and anxiety/depression.
- 4) the Stroke Impact Scale (SIS) assesses stroke-specific quality of life. The SIS is reliable, valid and sensitive to change.(33)

Balance and Mobility tests:

- 5) the Functional Ambulation Classification (FAC) classifies functional ambulation in patients undergoing physical therapy.(34),(35)
- 6) The Berg Balance Test (36) is a psychometrically sound measure of balance impairment for use in poststroke assessment. Given the floor and ceiling effects it is recommended that it is used in conjunction with other balance measures.
- 7) the 4-Square Step Test (37) is a reliable and valid clinical test of dynamic standing balance with high sensitivity and specificity.
- 8) the 5-Times Sit-to-Stand Test (38) is a functional mobility test that has excellent reliability as a measurement tool that correlates with knee flexors muscle strength.(39) (40)

All assessments will be conducted by an experienced physiotherapist.

During the intervention period the participants will be monitored for their adherence to the group exercise programme (attendance register kept by the therapists). The participants will also be asked to keep a record of the time they spend on their home exercise programme, and their fall events (with subsequent injuries) during the intervention period (self-reported through diary, see Appendix 3).

Quantitative data collection

During the outcome assessment participants will be individually interviewed about their experiences with the programme by an experienced physiotherapist who was not involved in delivering the FallMAP sessions. Family members involved with the patient will also be invited to consent (see Appendix 4) an interview. The Patient Information Statement for the family members can be found in Appendix 5.

Depending on the group a one-hour focus group may be undertaken. The topics guide for the interviews can be found in Appendix 6.

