As described in the risks paragraph above, expected adverse events during participation in this study include the following:

- slips, trips and falls and its consequences: cuts and abrasions, soft tissue injury, fracture.
- muscular/joint pain associated with the above or with increased physical activity.

All AEs judged by the reporting exercise instructor as having reasonable causal relationship to a study procedure or the intervention qualifies as a 'related AE'. The expression "*reasonable causal relationship*" means to convey in general that there is evidence or argument to suggest a causal relationship. An assignment of causality should be made by the exercise instructor responsible for conducting the FallMAP sessions using the definitions in the table below. All AEs judged as having a reasonable suspected causal relationship to a study procedure or the intervention (i.e. definitely, probably or possibly related) are considered to be related AEs. If required, the opinion of the participant's own GP will be sought. In the case of discrepant views on causality between the investigator and others, all parties will discuss the case. In the event that no agreement is made, Curtin University's HREC will be informed of both points of view.

| Relationship | Description |
|---------------------|--|
| Unrelated | There is no evidence of any causal relationship |
| Unlikely | There is little evidence to suggest there is a causal relationship (e.g. the event did not occur within a reasonable time after administration of the study procedure). There is another reasonable explanation for the event (e.g. the participant's clinical condition, other concomitant treatment). |
| Possible | There is some evidence to suggest a causal relationship (e.g. because the event occurs within a reasonable time after administration of the study procedure). However, the influence of other factors may have contributed to the event (e.g. the participant's clinical condition, other concomitant treatments). |
| Probable | There is evidence to suggest a causal relationship and the influence of other factors is unlikely. |
| Definitely | There is clear evidence to suggest a causal relationship and other possible contributing factors can be ruled out. |
| Not assessable | There is insufficient or incomplete evidence to make a clinical judgement of the causal relationship. |

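### Does safety progression criterion 2 need a new causality rule because, with 10 participants, one rating can decide it?

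*Combined protocol and SAP*

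**What the plan says.** Section 7, under the assessment of feasibility to progress, sets two criteria. The second requires less than 10% "of serious adverse events (SAEs) deemed due to the intervention". It names no rater, no rating cut-off and no denominator. Section 6 fixes the size: "A convenience sample of 10 patients after stroke will be recruited".

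Section 9 supplies most of the rest:

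- **Rater.** "An assignment of causality should be made by the exercise instructor responsible for conducting the FallMAP sessions", on a six-level table.
- **What counts as related.** Events judged as "having a reasonable suspected causal relationship to a study procedure or the intervention (i.e. definitely, probably or possibly related".
- **Not assessable.** A separate level, described as "There is insufficient or incomplete evidence to make a clinical judgement of the causal relationship". It is not on the related list.
- **Checks.** The participant's general practitioner may be consulted. Discrepant views between the investigator and others are discussed by all parties. If they still disagree, the "HREC will be informed of both points of view".
- **Review.** The chief investigator and the instructors discuss recorded events. Related events go to all investigators and the ethics committee within five working days.

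**The concern.** At this sample size the safety criterion is in effect a zero-event rule, so the label on one SAE decides it. Several features of that label look loose. The person who rates the event also delivers the sessions, whereas the participant interviews are held "by an experienced physiotherapist who was not involved in delivering the FallMAP sessions". The dispute process ends in a report, not a decision. Criterion 2 speaks of events due to the intervention, whereas section 9 defines related events as those linked to the intervention or to a study procedure. An SAE with too little evidence drops out of the count without comment. The last two features can only lower the count, so they lean towards a pass.

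This is the only safety criterion of the two, for a programme that teaches people after stroke how to fall. Falls and fractures are listed as expected events. A hospital admission after an unwitnessed fall at home is easy to imagine, and views on its cause could differ. If the plan left such events open, two teams could reach opposite verdicts on the same facts.

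**Working it through.** **Inputs.** n = 10 (section 6); threshold below 10% (section 7); ratings and dispute steps (section 9). The plan derives no sample size, power or error rate, so there is no planned figure to reproduce. It gives no SAE rate and no share of disputed ratings.

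**Step 1: one event.**

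- Per participant: 0/10 = 0%, met; 1/10 = 10.0%, not below 10%, not met. With 9 or 8 participants, one event is 11.1% or 12.5%, also not met.
- Per SAE: one counted event among m SAEs passes only if 1/m < 0.10, so from m = 11 (1/11 = 9.1%). With no SAEs the natural reading is that the criterion is met.
- The two readings part only with 11 or more SAEs among ten people. If the number of SAEs is Poisson with an assumed mean of 2, that has probability 8.3 × 10⁻⁶. The unstated denominator therefore changes no realistic decision.

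One rating can indeed decide the criterion.

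**Step 2: which events are left unplaced?**

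| SAE | Section 9 | Criterion 2 on its own words |
|---|---|---|
| Definitely, probably or possibly due to the programme | Related | Counted |
| Unlikely or unrelated | Not related | Not counted |
| Not assessable | Not on the related list | Not counted |
| Due only to a study procedure, such as a balance test | Related, so reported | Not due to the intervention, so not counted |
| Still disputed after discussion | Both views go to the ethics committee | Open |

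The list in section 9 is introduced as exhaustive, and the section separates procedure from intervention. Two teams applying it would agree on the first four rows. Only the last row is open.

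**Step 3: how often could the open row decide?** Assume m SAEs on average (Poisson), a share r clearly due to the programme and a share q disputed to the end. The verdict rests on a disputed SAE with probability

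exp(−m·r) × (1 − exp(−m·q)).

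With r = 0.10 and q = 0.05:

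- m = 0.5: 0.951 × 0.025 = 2%
- m = 1: 0.905 × 0.049 = 4%
- m = 2: 0.819 × 0.095 = 8%

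Raising q to between 0.10 and 0.40 gives 5–17%, 9–30% and 15–45%. Shares that high come from pooling true disputes with procedure-only and not-assessable events, which step 2 shows are already placed. Every input here is an assumption, and the conclusion does not rest on these figures.

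**Step 4: what can the criterion carry?** For a true risk p per participant of a counted SAE, the chance of failing is 1 − (1 − p)¹⁰: 9.6% at p = 1%, 18.3% at 2%, 40.1% at 5% and 65.1% at 10%. So it fails about one time in ten when the risk is 1%, and passes about one time in three (34.9%) when the risk is 10%. After 0 of 10, the one-sided 95% upper limit is 1 − 0.05^(1/10) = 25.9%. A firmer rating rule would not improve that.

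**Step 5: time window.** Section 6 states "The sessions will be offered over a period of 8 weeks", alternating one and two sessions a week: 4 × (1 + 2) = 12 sessions. Section 9 refers to 12 weeks of participation. Adding the baseline week and the one-week outcome window to the 8 weeks gives about 10. The passages need reconciling. Neither sets a window for criterion 2, and SAEs are collected by questions before each session and from the diaries, so in practice the count follows that collection.

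**The case for a change.** The best case for a change is that the rule should be fixed before any event occurs, because a rule chosen afterwards is chosen with the verdict in view. The cost looks small: a cross-reference to section 9, a named person for the final rating, and a statement on disputed and not-assessable SAEs. The plan already uses someone outside delivery for the interviews, so the principle is not foreign to it.

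Part of this stands. Section 9 names no deciding view, and criterion 2 does not borrow the term it defines. The review by the chief investigator is also worded so that it may cover only SAEs already rated as related. On that reading, an SAE the instructor rates as unlikely would not reach that discussion automatically. Against this, every reported SAE is recorded and assessed for causality and seriousness, and the section expressly foresees that the investigator may disagree.

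The rest is weaker. An outside interviewer protects candour about the programme, which is a different purpose from judging the cause of an event. The plan identifies nobody who neither delivers sessions nor administers tests, so the extra rater is not free. Counting every unresolved SAE as due to the intervention would make the criterion stricter. That is a policy choice, not the repair of an error.

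**Conclusion.** The observation is correct, but no change follows. With 10 participants, one SAE moves criterion 2 from 0% (met) to 10% (not met), and the rating starts with the session instructor. However, the plan does say which ratings count, it limits the criterion to the intervention, and it exposes the rating to challenge.

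What remains is one gap: an SAE whose cause is still disputed after discussion, when no other SAE already fails the criterion. Analysts would fill it sensibly by describing the event, giving both views as the ethics committee receives them, and stating the result both ways. The analysis is descriptive, the criteria sit within a team discussion that informs a later trial, and no automatic stop is attached. Any single SAE among ten people would be weighed on its facts in that discussion.

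This rests on reading the related list in section 9 as closed and on SAEs being few. How often the gap would matter cannot be known from the documents: on assumed inputs with 5% of SAEs disputed to the end, about 2–8% of such studies. The mismatch between 8 and 12 weeks is an editorial point, with no shown effect on the criterion.
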